11.6.4 Safety Evaluation

Safety variables monitored in this study include: AEs; vital signs (systolic and diastolic blood pressure, pulse rate, respiratory rate); spirometry; ECG data; concomitant medication, clinical chemistry, hematology, urine analysis safety panel, BMI, physical examination, respiratory symptoms (cough assessment VAS and Likert scales).

The primary analysis of Safety parameters will be conducted on the Safety population as described in Section 11.1.3 “Descriptive Statistics”.

11.6.4.1 Safety Reporting

An exposure emergent AE is defined as an AE that occurs after first product use or that is present prior to first product use and becomes more severe after first product use. All other AEs will not be summarized but provided in listings only.

Any AEs which occur during the Screening Period will be captured by the site collaborators and assessed by the Investigator or designee in order to establish relationship or relatedness in respect to study procedures. All collected AEs will be reported in the CSR and will be in accordance with the respective regulatory guidelines. The AE listings will include all AEs captured in the database at any time during the study (including those from subjects who were not in the safety population). All AEs occurring after the product test of CHTP 1.1 M or mCC will be included in the summary tables. During the screening period prior to the first CHTP 1.1 M or mCC product use, only study procedure related AEs will be listed only.

AEs reported from enrolled subjects, but not started use on day 1 or later will be summarized in a separate sequence: "Enrolled but not started randomized product use". Furthermore AEs reported after discharge (Day 4) are summarized in a separate sequence 'safety follow-up'.

If there are more than 10 AEs, the tables will also be split by study period. The study periods will be defined as in **Table 15**:

Table 15: Study Periods

Period	Period Start	Period End
Screening	Date of informed consent	Day -4
CHTP 1.1 M Product Test	Day -3	Day -1
Study Period 1	Day 1	Day 2
Study Period 2	Day 3	Day 4
Safety Follow-Up	Day 5	EOS

Partial dates will not be imputed, but assumptions will be made as follows to assign to exposure-emergent or not:

Date information	Assign as
Partial date, e.g., --May2012, or ----2011. If month/year is the same as, or later than the month and/or year of first product use	Exposure-emergent
Partial date, e.g., --May2012, or ----2011. If month and/or year is earlier than the month and/or year of first product use	Not exposure-emergent

If exposure emergent adverse events cannot be attributed to CHTP 1.1 M / mCC due to e.g. missing start time, the worst case principle will be applied : i.e. the event will be allocated to CHTP 1.1 M use.

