6 INVESTIGATIONAL PLAN

6.1 Study Design

[figure not shown]
This is a randomized, controlled, 2-period, 2-sequence, single-use crossover study. Each subject will receive CHTP 1.1 M and mCC (Figure 1 Study Flow Chart).

The end of the study is defined as the date when the last subject completes his/her 7-day safety follow-up period.

Subjects that terminate the study after Enrolment and prior to completion of the study will be asked to undertake early termination procedures.

1) Screening and Admission (from the ICF Signature to the Enrolment at Admission):

A Screening Visit will be conducted within 4 weeks (Day -31 to Day -4) prior to Admission to the investigational site (Day -3). A demonstration of the CHTP 1.1 M will be done by the site collaborators during the Screening Visit. Screening procedures do not necessarily have to be conducted on the same day. On Day -3 (Admission), after all inclusion/exclusion criteria are checked, all eligible subjects will be enrolled and perform a product test using 3 to 5 CHTPs 1.1 M. After product test, subjects not ready to use the CHTP 1.1 M will be discontinued. All subjects that are not enrolled are considered as screen failures. Subject will be instructed not to smoke in the morning prior to Admission. After Admission, smoking will not be allowed until blood drawing for the assessment of CYP2A6 activity and spirometry have been performed (Section 9.2). After these assessment procedures, smoking will be allowed until 11.00 PM at Admission.

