**Figure 1 Study Flow Chart****2) The Investigational Period (from Day -2 to Discharge):**

The Investigational period will consist of 2 periods (Period 1, Period 2) with each period consisting of approximately 48 to 57 hours smoking abstinence and 1 day of single product use.

Period 1: From Day -2 to Day 1. After Day 1 product use, the subject will start his/her washout for period 2

Period 2: From Day 2 to Day 3. The products should be used at the same time (within 1 hour) on Day 1 and Day 3

48 eligible, healthy smoking subjects will be randomized to one of 2 sequences:

Table 1 Definition of Randomization Sequences

Sequence	Sample Size
1. CHTP 1.1 M then mCC	24
2. mCC then CHTP 1.1 M	24

Each sex and smoking strata (International Organization for Standardization [ISO] nicotine levels ≤ 0.6 mg vs. >0.6 to 1.0 mg) will have a quota applied to ensure they represent at least 40% of the study population for each Sequence (Sequence 1 and Sequence 2).

Subjects who do not complete the study after randomization will not be replaced.

Subjects will be discharged from the investigational site in the morning of Day 4 after performance of Discharge assessments.

3) The Safety Follow-up Period (from Discharge until Day 11):

A 7-day safety follow-up will be done for the recording of spontaneously reported AEs and SAEs (passive surveillance) and the active follow-up by the investigational site of AEs/SAEs ongoing at Discharge. Any AE will in general be followed-up until resolved, stabilized (*i.e.*, no worsening of the event), or until a plausible explanation for the event has been found.

The end of study for the subject is defined as the date of completion or discontinuation on Subject status form completed. AEs/SAEs not resolved or not stabilized at EOS are to be recorded as ongoing at EOS.

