9 CHANGES FROM THE PROTOCOL SPECIFIED STATISTICAL ANALYSIS

The analyses of Adverse Events will be performed by sequence; and by sequence and period if there are more than 10 AEs. The other safety evaluations will also analyzed by sequence and study day.

Shift tables for safety endpoints will not be produced for this study, because the relevant information will be provided in listings.

Statistical analysis for blood COHb (%) and exhaled CO (ppm) measurements and the QSU-brief questionnaire data will be performed including interaction terms for product and time point to enable LS means to be calculated at each time point in order to explore the pattern of the CHTP 1.1 M effect over time. The main comparison between products will be the comparison over all time points.

Serology for human immunodeficiency virus (HIV) 1/2 cannot be transferred because of privacy laws, therefore this endpoint is not presented in listings.

In addition to the PK parameters mentioned in the protocol, %AUC_{extrap} will be listed, as this parameter contains important information on the quality of the AUC_(0-∞).

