10 ANALYSIS POPULATIONS

For analysis purposes, actual product exposure during single use days will be defined as:

- CHTP 1.1 Menthol: if there is a non-missing time for “Time of First Puff” (from CHTP 1.1 Menthol consumption page in eCRF), and no other product exposure definition is applicable.
- mCC: if there is a non-missing “Time of lighting the mCC” (from mCC product consumption eCRF page), and no other product exposure definition is applicable.

All analyses will be based on actual product exposure. All endpoints (other than safety) will be analyzed using the PK Analysis sets. Safety will be analyzed using the safety population.

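### Table 15 bounds the AE study periods by whole day: it conflicts with the SAP's own start of follow-up on Day 4, and puts events before T0 on Day 3 (and, more mildly, Day 1) in the cell of a product not yet used in that period

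*SAP*

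**What the plan says.** All references are to the SAP.

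- Section 9 states the layout of the AE tables: "The analyses of Adverse Events will be performed by sequence; and by sequence and period if there are more than 10 AEs". Section 11.6.4.1 repeats the trigger, "If there are more than 10 AEs, the tables will also be split by study period", and refers to Table 15 for the period definitions.
- Table 15 gives five periods in whole days: screening up to Day -4; CHTP 1.1 M product test, Day -3 to Day -1; Study Period 1, Day 1 to Day 2; Study Period 2, Day 3 to Day 4; safety follow-up, Day 5 to end of study. No clock time and no T0 appears.
- The text of the same section says that "AEs reported after discharge (Day 4) are summarized in a separate sequence", labelled safety follow-up.
- Section 6.1 places discharge in the morning of Day 4 and heads the next phase "The Safety Follow-up Period (from Discharge until Day 11". The schedule in Section 15.1 shows follow-up as Day 4 to Day 11.
- Section 11.1.4 defines T0 as the first puff on Day 1 and on Day 3. Section 10.5.2.1 requires it between 06:00 and 09:00, within 1 hour of the same time on both days.
- Section 4 defines the first product use time point as the start of the product test, which Section 6.1 places on Day -3. An AE before T0 on Day 1 or Day 3 can therefore already be exposure-emergent and be tabulated.
- Section 11.6.4.1 has a fallback that allocates the event to CHTP 1.1 M: "If exposure emergent adverse events cannot be attributed to CHTP 1.1 M / mCC due to e.g. missing start time".

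**The concern.** In a two-sequence, two-period crossover, each cell of sequence by period stands for one randomized product. A reader of the split AE tables will take the Study Period 2 column of the CHTP 1.1 M – mCC sequence as events on mCC. That reading holds only if the period starts when the product is used. Table 15 starts it at midnight, 6 to 9 hours too early.

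Those hours are not empty. Section 10.5.2.1 places the cough assessment before product use, and the first nicotine sample, COHb sample, CO breath test and QSU-brief within 15 minutes before T0.

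On Day 4 the SAP gives two instructions for the same event, and programmers following different lines of Section 11.6.4.1 would produce different counts. AE incidence is a listed safety endpoint (Section 5.2), and the affected tables include some that go to the medical safety officer and into the topline results (Sections 12.2 and 12.3).

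**Working it through.** The SAP gives no figure to reproduce here. The check compares the passages and adds clock arithmetic.

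**Where an event lands.** Onset times are illustrative.

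| Onset | Latest exposure before onset | Cell under Table 15 | Cell if cut at T0 and discharge |
|---|---|---|---|
| Day 1, 03:00, sequence 1 | CHTP 1.1 M test and own mCC on Day -3 | Study Period 1 (CHTP 1.1 M) | Product test/wash-out |
| Day 1, 03:00, sequence 2 | CHTP 1.1 M test and own mCC on Day -3 | Study Period 1 (mCC) | Product test/wash-out |
| Day 3, 03:00, sequence 1 | CHTP 1.1 M on Day 1 | Study Period 2 (mCC) | Study Period 1 (CHTP 1.1 M) |
| Day 3, 03:00, sequence 2 | mCC on Day 1 | Study Period 2 (CHTP 1.1 M) | Study Period 1 (mCC) |
| Day 4, after discharge | Day 3 product; subject discharged | Study Period 2 by the table, safety follow-up by the text | Safety follow-up |

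The Day 3 rows change the product in both sequences. The Day 1 rows are milder. In sequence 1 the product is the same as the test product. In both sequences the preceding interval already mixes exposures, because on Day -3, after the CYP2A6 blood draw and spirometry, "smoking will be allowed until 11.00 PM at Admission".

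**Size of the Day 3 window.** Let h1 and h3 be the clock hours of T0 on Day 1 and Day 3, each between 6 and 9 and at most 1 apart. The time between uses is 48 − h1 + h3 hours, of which h3 hours lie after midnight on Day 3 and before T0.

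Share = h3 / (48 − h1 + h3)

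- h1 = h3 = 6: 6/48 = 12.5% (minimum)
- h1 = h3 = 9: 9/48 = 18.75% (maximum)
- T0 one hour apart: 6/47 = 12.8% (h1 = 7, h3 = 6) and 9/49 = 18.4% (h1 = 8, h3 = 9), both inside the range

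On Day 1 the hours before T0 are 6 to 9 of the 48 in Study Period 1, again 12.5% to 18.75%.

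**Size of the Day 4 conflict.** Only the morning is stated for discharge, so I assume 06:00 to 12:00. The hours of Day 4 left after discharge are 24 − 6 = 18 down to 24 − 12 = 12. Against the 48 hours of Study Period 2 that is 18/48 = 37.5% down to 12/48 = 25%.

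**The case against.** **Table 15 names no product.** This is true: the link to product comes only from crossing period with sequence. The missing-start-time fallback also suggests that attribution by start time was intended. A reader might therefore infer that the SAP deliberately assigns events before T0 to the later product; the documents do not go that far. What stands is that no clock-time rule is written, and that Table 15 followed literally gives the wrong cell.

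**Day 2.** Section 6.1 says "Period 2: From Day 2 to Day 3", while Table 15 puts Day 2 in Study Period 1. A reader might infer a second contradiction of the same kind as Day 4. It is not one: Section 11.6.4.1 expressly defines the AE periods by Table 15, and Section 6.1 describes design periods made up of abstinence plus a use day. Keeping Day 2 with the Day 1 product also fits the 24-hour nicotine sample and the cough assessment timed from T0 of Day 1. Only the shared name needs clarifying.

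**By-product tables.** Section 10 says "All analyses will be based on actual product exposure", and one might infer that the by-sequence AE tables break that promise when there are 10 or fewer AEs. In context the sentence follows definitions of actual exposure, so it sets an as-used rule and does not promise product columns. Reporting safety by sequence is a declared choice (Sections 9 and 11.1.3), and AEs by relatedness to product are tabulated whatever the count (Section 11.6.4.2). An additional by-product table would be a preference, not a correction.

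**Small effect.** The split is descriptive and conditional, procedure-related AEs have their own table, and every AE is listed. This stands and sets the weight of the point, but a listing does not correct a count in the wrong column.

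**Conclusion.** The Day 4 conflict is certain: Section 11.6.4.1 disagrees with itself, and Section 6.1 and the schedule support its text against Table 15. The missing T0 boundary is equally plain. Its consequence for product rests on reading each cell of sequence by period as one randomized product, which the crossover design implies.

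The percentages are shares of clock time. A reader might take 12.5% to 18.75% as the proportion of AEs misplaced; the SAP gives no AE rate or onset pattern, so no such proportion can be derived. The 12 to 18 hours on Day 4 depend on the assumed discharge time.

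The misplaced cells arise only in descriptive AE tables split by period, produced when there are more than 10 AEs. No confidence interval and no primary PK result changes. Severity: minor.

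**What to change.** - Redraw Table 15 with limits at the start of the product test, T0 of Day 1, T0 of Day 3 and the time of discharge.
- Align the safety follow-up row with the text on events after the Day 4 discharge, and say whether onset or reporting decides, since the text speaks of reported events.
- State that the existing CHTP 1.1 M worst-case rule applies when a start time is missing. On Day 3 that selects Study Period 1 in sequence 1 and Study Period 2 in sequence 2. Where the rule does not choose between products (Day 1 in sequence 1, Day 4 in sequence 1), add a default.
- Note that the AE study periods differ from the design periods of Section 6.1, with Day 2 kept with the Day 1 product for AEs.

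The cost is a few lines of SAP text and a change to the period derivation. No new table is needed. T0 is collected, and the fallback rule presupposes AE start times. The SAP does not say whether the clock time of discharge is captured; if it is not, name a proxy such as the last discharge assessment.

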11.6.4.2 Adverse Events

A general summary table of AEs will be presented by sequence (and period if more than 10 AEs) and overall, including:

- The number of events and the number and percentage of subjects reporting at least one AE.
- The number of events and the number and percentage of subjects reporting at least one AE leading to death.
- The number of events and the number and percentage of subjects reporting at least one study product –related AE, broken down by product relatedness (related to CHTP 1.1 M / mCC) and expectedness (expected, not expected).
- The number of events and the number and percentage of subjects reporting at least one AE broken down by severity, including a subject once with worst severity.
- The number of events and the number and percentage of subjects reporting at least one AE leading to any action taken, broken down by action taken related to the product (combining the following items: product use interrupted, product use reduced, product use stopped), treatment given (yes, no), study discontinuation, other action taken.
- The number of events and the number and percentage of subjects reporting at least one AE related to study procedure.

Additional summary tables of AEs will be presented by sequence (and period if more than 10 AEs) and overall, with a breakdown of the number of events, as well as the number and percentage of subjects reporting each AE, categorized by SOC and PT coded according to the MedDRA dictionary (version 18.0):

- The number of events and the number and percentage of subjects reporting at least one AE.
- The number of events and the number and percentage of subjects reporting at least one AE leading to death.
- The number of events and the number and percentage of subjects with at least one AE related to product exposure and expectedness for investigational product (IP;CHTP 1.1 M or mCC).
- The number of events and the number and percentage of subjects with at least one AE leading to study discontinuation.
- The number of events and the number and percentage of subjects with at least one AE related to study procedure.
- The number of events and the number and percentage of subjects with at least one AE by severity (mild, moderate, severe)

If a subject has more than one occurrence of the same AE, the subject will be counted only once within a PT for each sequence, with the worst occurrence based on the presentation (e.g., for presentation by severity = most severe, for presentation by relationship = most related). Missing information on the intensity of AE will be counted as severe.

The data will be presented in the below outputs:

TFL number	Title
TABLES	
15.2.6.1	Summary of Adverse Events – Safety Population
15.2.6.2.1	Summary of Adverse Events by System Organ Class and Preferred Term – Safety Population
15.2.6.2.2	Summary of Adverse Events by System Organ Class – Safety Population
15.2.6.2.3	Summary of Adverse Events by Preferred Term – Safety Population
15.2.6.3	Summary of Adverse Events by System Organ Class, Preferred Term and Relationship to Study Product Exposure for Investigational Product (CHTP 1.1 M or mCC)– Safety Population
15.2.6.4	Summary of Adverse Events Leading to Study Discontinuation by System Organ Class and Preferred Term – Safety Population
15.2.6.5	Summary of Adverse Events by System Organ Class, Preferred Term and Severity – Safety Population
15.2.6.6	Summary of Adverse Events Related to Study Procedure by System Organ Class and Preferred Term – Safety Population
LISTINGS	
15.3.6.1.1	Listing of Adverse Events

11.6.4.2.1 Serious Adverse Events (Including Deaths)

A general summary table of SAEs will be presented by sequence (and period if more than 10 AEs) and overall, including the number of events and the number and percentage of subjects reporting at least one SAE.

SAEs will be listed in separate listings by sequence.

The data will be presented in the below outputs:

TFL number	Title
TABLES	
15.2.6.1	Summary of Adverse Events – Safety Population
LISTINGS	
15.3.6.1.2	Listing of Serious Adverse Events

11.6.4.2.2 Adverse Events Leading to Withdrawal

Summaries will be presented for AEs leading to withdrawal, by sequence (and period if more than 10 AEs) and overall AEs leading to withdrawal will also be listed in separate listings by sequence.

The data will be presented in the below outputs:

TFL number	Title
TABLES	
15.2.6.1	Summary of Adverse Events – Safety Population
LISTINGS	
15.3.6.1.3	Listing of Adverse Events Leading to Discontinuation

11.6.4.2.3 Laboratory Abnormalities

Laboratory abnormality data will be listed ordered by sequence, subject and time point. Details related to the toxicity grading of laboratory abnormalities are available in Section 11.6.4.4 “Clinical Laboratory Evaluation”.

TFL number	Title
LISTINGS	
15.3.6.4	Listing of Clinical Chemistry Data, Shift, Changes from Baseline and CTCAE grades
15.3.6.5	Listing of Hematology Data, Shift, Changes from Baseline and CTCAE grades
15.3.6.6	Listing of Urinalysis Data, Shift, Changes from Baseline and CTCAE grades
15.3.6.1.3	Listing of Adverse Events Leading to Discontinuation

11.6.4.3 Investigational Product Malfunction and Misuse

All events relating to CHTP 1.1 M Malfunction and Misuse will be listed for each subject, including event description and onset datetimes.

A summary table of CHTP 1.1 M Malfunction and Misuse will be presented by sequence and overall, including:

- Number of CHTP 1.1 M Malfunction and Misuse events and the number and percentage of subjects reporting at least one event.
- Number of CHTP 1.1 M Malfunction and Misuse events and the number and percentage of subjects categorized by event description (Defect CHTP 1.1 M before use, Defect CHTP 1.1 M during decapping, Defect CHTP 1.1 M during use, other)

CHTP 1.1 M Malfunction and Misuse events and inventory will be listed by sequence. Data collected during Screening will be listed but not summarized.

The data will be presented in the below outputs:

TFL number	Title
TABLES	
15.2.6.7	Summary of CHTP 1.1 M Malfunction and Misuse events– Safety Population
LISTINGS	
15.3.6.2	Listing of CHTP 1.1 M Malfunction and Misuse events

11.6.4.4 Clinical Laboratory Evaluation

Table 16 lists the hematology, clinical chemistry, and urine analysis parameters to be assessed in this study.

Table 16: List of Laboratory Safety Parameters

Hematology	Clinical chemistry	Urine analysis
Hematocrit	Albumin	pH
Hemoglobin	Total protein	Bilirubin
Mean corpuscular hemoglobin	Alkaline phosphatase	Glucose
Mean corpuscular hemoglobin concentration	Alanine aminotransferase	Nitrite
Mean corpuscular volume	Aspartate aminotransferase	RBC traces
Platelet count	Blood urea nitrogen	Protein
Red blood cell (RBC) count	Creatinine	Specific gravity
White blood cell (WBC) count	Gamma-glutamyltransferase	
Differential WBC count:	Fasting glucose	
• Neutrophils	Lactate dehydrogenase	
• Basophils	Potassium	
• Eosinophils	Sodium	
• Lymphocytes	Total bilirubin	
• Monocytes	Direct bilirubin	
	Total cholesterol	
	Triglycerides	

Any clinical safety laboratory test result that is outside of the normal reference range will be reviewed by the PI and assessed for clinical relevance. If the PI considers the abnormal result to be of clinical relevance, then it must be recorded as a concomitant disease at Screening, or if not present at Screening, as an AE during the study. If the condition worsens after screening it will be recorded as an AE.

The grading scheme used in the Common Terminology Criteria for Adverse Events and Common Toxicity Criteria [CTCAE] version 4.03) will be used by the PI to assess abnormal laboratory AEs. These CTCAE grades will be derived programmatically in the creation of the SDTM datasets.

Laboratory data will be summarized and listed at screening, baseline (Admission, Day -3) and at discharge (Day 4 or at the day of withdrawal), together with changes from baseline. The number and percentage of subjects with normal results, high/low results and abnormal clinical result (as defined by PI comment) will be tabulated for laboratory parameters.

Listings for the clinical laboratory data will include the following information: normal/high/low (with respect to the reference range), abnormal clinically relevant (as defined by the PI comments), the PI comments, the change from baseline and the CTCAE grade. Only CTCAE grades greater than zero will be presented.

The data will be presented in the below outputs:

TFL number	Title
TABLES	
15.2.6.10	Summary of Clinical Chemistry Parameters – Safety Population
15.2.6.11	Summary of Hematology Parameters – Safety Population
15.2.6.12	Summary of Urinalysis Parameters – Safety Population
LISTINGS	
15.3.6.4	Listing of Clinical Chemistry Data, Shift, Changes from Baseline and CTCAE grades
15.3.6.5	Listing of Hematology Data Shift, Changes from Baseline and CTCAE grades
15.3.6.6	Listing of Urinalysis Data Shift, Changes from Baseline and CTCAE grades

